11.2.2. Investigator Skin Assessments

The investigator skin assessment will be made at each in clinic visit starting at month 1. The entire surface area of the outer upper arm from the upper shoulder to the elbow will be assessed for the following skin signs or symptoms.

Investigator reported skin bruising, skin redness (erythema), and skin swelling (edema) at the application site will be collected and will also be recorded in the eCRF.

The amount of bruising, erythema, and edema and the presence of skin signs and symptoms will be categorized and assessed as follows:

Skin signs or symptoms	Indicate arm assessed: Subject's Left and/or Right (circle)
Blisters or pustules?	Present: Yes or No If Yes, describe:
Scaly or flakey skin?	Present: Yes or No If Yes, describe:
Erosions or open sores?	Present: Yes or No If Yes, describe:
Scarring?	Present: Yes or No If Yes, describe:
Hyperpigmentation or Hypopigmentation?	Present: Yes or No If Yes, describe:

Bruising assessments (visual rating) will be performed using the following ratings:

Symptom	Rating (circle)
M207 application sites have bruising spots?	0 (clear) = None 1 (mild) = ≤ 25% Present in the upper arm region of all M207 applications 2 (moderate) = ≥ 26 to ≤ 50% Present in the upper arm region of all M207 applications 3 (severe) = > 50% Present in the upper arm region of all M207 applications

Erythema Severity Categories:

Symptom	Rating (circle)
Skin Erythema	0 (clear) = None 1 (mild) = ≤ 25% Present in the upper arm region of all M207 applications 2 (moderate) = ≥ 26 to ≤ 50% Present in the upper arm region of all M207 applications 3 (severe) = > 50% Present in the upper arm region of all M207 applications

Edema Severity Categories:

Symptom	Rating (circle)
Skin Edema	0 (clear) = None 1 (mild) = ≤ 25% Present in the upper arm region of all M207

	
applications
 
2 (moderate) = ≥ 26 to $\leq 50\%$ Present in the upper arm region of all M207 applications
 
3 (severe) = $> 50\%$ Present in the upper arm region of all M207 applications

--	---

The frequencies of amount of bruising, erythema, and edema at the application site as assessed by the Investigator at Months 1, 2, 3, 6, 9, 12, and at the 2-week post-study visit will be summarized. The proportion of subjects with any amount of all 3 symptoms (erythema, edema, and bruising) and all combinations of the 3 symptoms will be summarized by time point.

The proportions of subjects with presence of skin signs and symptoms as assessed by the Investigator at Months 1, 2, 3, 6, 9, 12, and at the 2-week post-study visit will also be summarized.

All investigator skin assessments will also be listed.

11.3. LABORATORY EVALUATIONS

The lab results for clinical laboratory categories including hematology, serum chemistry as well as results for urine drug screens and serum and urine pregnancy tests will be recorded on the eCRF at the study visits mentioned in Table 1. The parameters given in the Table 3 will be assessed.

Table 3: Clinical Laboratory Tests

Serum Chemistry	Hematology	Additional Tests
Glucose	Hematocrit	Serum (at screen visit only) and Urine Pregnancy (WOCBP only) ¹ ² Urine drug screens will test for: amphetamines, barbiturates, cocaine, cannabinoids, opioids, phencyclidine (PCP), and methamphetamines
Aspartate aminotransferase (AST)	Hemoglobin	
Alanine aminotransferase (ALT)	Red Blood Cell Count	
Alkaline phosphatase (AP)	White Blood Cell Count with Differential	
Lactate dehydrogenase (LDH)	Platelet Count	
Sodium	Mean corpuscular volume	
Phosphorus	Mean corpuscular hemoglobin	
Potassium		

Serum Chemistry	Hematology	Additional Tests
Chloride	Mean corpuscular hemoglobin concentration	
Creatine phosphokinase (CPK)		
Globulin		
Cholesterol (HDL and LDL)		
Creatinine		
Blood urea nitrogen (BUN)		
Prothrombin (PT) and INR (International Normalized Ratio)		
Serum calcium		
Total bilirubin		
Triglyceride		
Gamma glutamyl transpeptidase (GGT)		
Serum glutamic pyruvic transaminase (SGPT)		
Serum glutamic oxaloacetic transaminase (SGOT)		
Uric acid		

Low, normal, and high classifications will be applied to determine whether the laboratory test value was below (low), within (normal), or above (high) its reference range. The number and percentage of subjects with indicated shifts (low, normal, high) in their results from baseline to post-baseline will be presented.

Separate listings will be produced for each laboratory test group (hematology, serum chemistry, urine drug screens, and serum and urine pregnancy tests). A listing of all abnormal results will be provided.

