- Screening procedures may be performed in 1 to 7 days
- Run-in period for 2 (+ up to 1) weeks prior to Day 1
- Clinic visits include Screening, drug dispensation visit Day 1, Month 1, 2, 3, 6, 9, 12 (or early discontinuation)
- A minimum of 2 migraine attacks treated per month with subject skin assessment recordings at 30 minutes, 2 hours, 12 hours, 24 hours and 48 hours post patch application

**STATISTICAL
ANALYSES**

The safety population will include all subjects who received any amount of study drug (i.e., applied at least 1 patch). Adverse events will be summarized overall and by preferred term and system organ class. Adverse events will also be summarized by severity and relationship to study drug. Serious AEs and AEs leading to discontinuation of study drug will also be summarized. Actual values and changes from baseline for clinical laboratory test results and vital sign measurements will be summarized using descriptive statistics (n, mean, SD, median, minimum, and maximum). ECG parameters will be summarized using shift tables. The number and percentage of subjects experiencing Bruising, Erythema, and Edema and other skin assessments will be tabulated.

All efficacy endpoints will be summarized using descriptive statistics. Further details regarding efficacy analyses can be found in the statistical analysis plan.

TABLE OF CONTENTS

PROTOCOL SIGNATURE PAGE - PRINCIPAL INVESTIGATOR	2
LIST OF ABBREVIATIONS AND DEFINITION OF TERMS	3
PROTOCOL SYNOPSIS	5
TABLE OF CONTENTS	11
LIST OF TABLES	14
LIST OF FIGURES	14
1 INTRODUCTION	16
1.1 Background.....	16
1.2 Clinical Pharmacology, Efficacy, and Safety of Zolmitriptan.....	17
1.2.1 Human pharmacokinetics.....	17
1.2.2 CP-2016-001 Clinical Efficacy and Safety Study.....	19
1.2.2.1 Primary Efficacy Analysis.....	20
1.2.2.2 Secondary Efficacy.....	21
1.2.2.3 Previous Co-Primary Endpoints in Migraine Trials for Comparison.....	22
1.2.2.4 Safety Results.....	24
1.3 Study Rationale.....	28
2 STUDY OBJECTIVES	29
2.1 Primary Objective.....	29
2.2 Secondary Objectives.....	29
3 INVESTIGATIONAL PLAN	30
3.1 Study Design.....	30
3.2 Selection of Study Population.....	31
3.2.1 Number of Subjects.....	31
3.2.2 Inclusion Criteria.....	31
3.2.3 Exclusion Criteria.....	33
3.2.4 Eligibility Criteria for Study Treatment.....	35
3.2.5 Prior and Concomitant Medications Allowed During the Study.....	36
3.2.6 Early Termination.....	36
3.2.6.1 Withdrawal of Subjects.....	36
3.2.6.2 Replacement of Subjects.....	37

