7.3.2 Safety Analyses

Safety will be assessed by the monitoring and recording of AEs, clinical laboratory tests, vital signs, physical examination findings, ECG parameters, and Investigator and subject reported skin assessments.

All safety analyses will be based on the Safety Population. Adverse events will be coded using the current Medical Dictionary for Regulatory Activities (MedDRA) dictionary (using the latest version) and will be summarized overall and by preferred term and system organ class. Adverse events will also be summarized by severity and relationship to study drug. Serious AEs and AEs leading to discontinuation of study drug will also be summarized.

Actual values and changes from baseline for assessments of clinical laboratory test results, ECG parameters, and vital sign measurements will be summarized at each visit using descriptive statistics (n, mean, SD, median, minimum, and maximum) or shift tables as appropriate. The number and percentage of subjects experiencing Bruising, Erythema, Edema and other skin assessments will also be summarized.

All data gathered will be listed by patient and parameter, separate listings of all abnormal laboratory findings will be provided, and clinically significant abnormalities will be recorded as AEs.

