4.2. SAFETY ENDPOINTS

- Changes from baseline in physical examination findings at Months 6 and 12
- Changes from baseline in vital signs at Months 1, 2, 3, 6, 9, 12, and at the 2-week post-study visit
- Changes from baseline in clinical laboratory parameters at Month 12
- Changes from baseline and/or shifts in 12-lead ECG parameters at Months 6 and 12
- Frequency of concomitant medications

- Incidence of treatment-emergent systemic and skin AEs (TEAEs)
- Frequencies of type of redness, severity of swelling, amount of bruising, and amount of bleeding (30 minutes only) at the application site as reported by the subject at 30 minutes, 2 hour, 12 hour, 24 hour, and 48 hours post-dose
- Frequencies of amount of skin itching and severity of pain at the application site as reported by the subject at 48 hours post-dose
- Frequencies of amount of bruising, erythema, and edema at the application site as assessed by the Investigator at Months 1, 2, 3, 6, 9, 12, and at the 2-week post-study visit
- Proportion of subjects with presence of skin signs and symptoms as assessed by the Investigator at Months 1, 2, 3, 6, 9, 12, and at the 2-week post-study visit

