6. GENERAL ASPECTS FOR STATISTICAL ANALYSIS

6.1. GENERAL METHODS

The statistical analysis will be conducted following the principles specified in the International Council for Harmonisation (ICH) Topic E9 Statistical Principles for Clinical Trials (CPMP/ICH/363/96).

All statistical tabulations and analyses will be done using SAS®, Version 9.4 or higher.

All results collected in the database will be presented in listings.

Unless otherwise stated, summary statistics including the number of subjects (n), mean, standard deviation (SD), median, minimum and maximum will be presented for continuous variables. Generally, the minimum and maximum values will be presented to the same decimal precision as the raw values, the mean and median values to one more, and the standard deviation, to two more decimal places than the raw values. This decimal place convention may be followed for all data elements. For categorical variables, per category, the absolute counts (n) and percentages (%) of subjects with data, and if appropriate, the number of subjects with missing data, will be presented. Percentages will be presented to one decimal place.

For adverse events, medical history and concomitant medications reported on a per-subject basis, the denominator for the percentage calculation will be the number of subjects at risk in each treatment group. A subject will be considered at risk if the subject is in the analysis set and in the subgroup of interest.

All p-values will be rounded to 4 decimal places. If a p-value is less than 0.0001 it will be displayed as “< 0.0001”.

Due to technical issues with the eDiary, any duplicate eDiary entries for a given time point will utilize the earliest recorded entry for analyses.

Unless otherwise specified all efficacy analyses will be based upon the modified intent-to-treat population and all safety as well as demographic and baseline characteristic analyses will be based upon the safety population.

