11. SAFETY

Safety will be assessed through the following:

- Physical examination findings including height (at screening and final visit only) and weight,
- Vital signs including blood pressure,
- Clinical laboratory determinations including serum chemistries and hematological parameters,
- 12-lead ECGs,
- Assessment of concomitant medications,
- All treatment-emergent systemic and skin AEs (TEAEs),
- Subject reported Skin Assessment, and
- Investigator Skin Assessment.

All safety analyses will be based on the Safety Population. Adverse events will be coded using the current Medical Dictionary for Regulatory Activities (MedDRA) dictionary (version 20.0 or higher) and will be summarized overall and by preferred term and system organ class. Adverse events will also be summarized by severity and relationship to study drug. Serious AEs and AEs leading to discontinuation of study drug will also be summarized.

Clinical laboratory test results and ECG parameters will be summarized at each visit using shift tables or listings of abnormal results as appropriate. The number and percentage of subjects experiencing Bruising, Erythema, Edema and other skin assessments will also be summarized.

All data gathered will be listed by patient and parameter, separate listings of all abnormal laboratory findings will be provided, and clinically significant abnormalities will be recorded as AEs.

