14.3.1.3a	Study Drug-Related Treatment Emergent Adverse Events by System Organ Class and Preferred Term - ALL Adverse Events Safety Set
14.3.1.3b	Study Drug-Related Treatment Emergent Adverse Events by System Organ Class and Preferred Term - E-Diary Skin Assessment Reported Adverse Events Safety Set
14.3.1.3c	Study Drug-Related Treatment Emergent Adverse Events by System Organ Class and Preferred Term - Other Subject Reported Adverse Events Safety Set
14.3.1.4	Serious Treatment Emergent Adverse Events by System Organ Class and Preferred Term-ALL Adverse Events Safety Set
14.3.1.5	Treatment Emergent Adverse Events of Special Interest by System Organ Class and Preferred Term- ALL Adverse Events Safety Set
14.3.1.6a	Treatment Emergent Adverse Events by Maximum Severity by System Organ Class and Preferred Term - ALL Adverse Events Safety Population
14.3.1.6b	Treatment Emergent Adverse Events by Maximum Severity by System Organ Class and Preferred Term - E-Diary Skin Assessment Reported Adverse Events Safety Population
14.3.1.6c	Treatment Emergent Adverse Events by Maximum Severity by System Organ Class and Preferred Term - Other Subject Reported Adverse Events Safety Population
14.3.2.1	Summary of Subject Reported Skin Assessment by Time After Patch Application Safety Population
14.3.2.2	Summary of Subject Reported Skin Assessment by Time After Patch Application - All Migraines Safety Population
14.3.2.3	Summary of Investigator Reported Skin Assessment by Visit Safety Population
14.3.2.4	Number of Treated Qualifying Migraines per Subject Safety Population
14.3.2.5	Number of Treated Qualifying Migraines per Month by Subject Safety Population
14.3.2.6	Number of Symptoms by Time Points - All Migraines Safety Population
14.3.3.1.1	Shift in Laboratory Tests: Hematology Safety Population
14.3.3.2.1	Shift in Laboratory Tests: Serum Chemistry Safety Population

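### The SAP keeps change from baseline in laboratory parameters as an endpoint but summarises laboratory data only as low/normal/high shifts, so no planned summary table shows the size of a change

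*SAP*

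**What the plan says.** SAP 4.2 names the endpoint as "Changes from baseline in clinical laboratory parameters at Month 12"; protocol 7.1.1 words it the same way. The statistical paragraph of the protocol synopsis says: "Actual values and changes from baseline for clinical laboratory test results and vital sign measurements will be summarized using descriptive statistics". It names n, mean, SD, median, minimum and maximum, and reserves shift tables for ECG parameters.

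Protocol 7.3.2 is looser. Actual values and changes for laboratory, ECG and vital sign data "will be summarized at each visit using descriptive statistics (n, mean, SD, median, minimum, and maximum) or shift tables as appropriate".

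The SAP then narrows this. Section 11 says: "Clinical laboratory test results and ECG parameters will be summarized at each visit using shift tables or listings of abnormal results as appropriate". Section 11.3 classifies each value against its reference range and states: "The number and percentage of subjects with indicated shifts (low, normal, high) in their results from baseline to post-baseline will be presented". It adds listings by test group and a listing of abnormal results. The index in SAP 17 holds two laboratory tables, 14.3.3.1.1 ("Shift in Laboratory Tests: Hematology Safety Population") and 14.3.3.2.1 ("Shift in Laboratory Tests: Serum Chemistry Safety Population"). The three indexed figures show skin scores. SAP 13 declares changes to efficacy endpoints only.

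**The concern.** A three-class shift table does not report a change in a continuous analyte. It loses two things.

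- **Size.** A value just above the upper limit and one several times the limit fall in the same cell, and a subject who is high at baseline and rises further is counted as high to high. The second case may arise here: exclusion criterion 13 removes subjects only above SGPT 150, SGOT 130 or LDH 750 U/L. If the laboratory's upper limits are lower than these (the documents do not give them), some subjects can enter already classed as high.
- **Group drift.** If the whole group moves a little within the reference range, few subjects cross a limit.

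Long-term safety is the primary objective. Chemistry and hematology are scheduled only at screening and at Month 12 or early termination, and SAP 6.1 keeps unscheduled results out of the summary tables. This single before-and-after comparison is therefore all that the laboratory summary tables can rest on.

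**Working it through.** **Reconciling the text.** The synopsis assigns descriptive statistics to laboratory data. Protocol 7.3.2 allows either form, so synopsis and body already differ. SAP 11 and 11.3 choose shifts and listings. SAP 6.1 has a default, "Unless otherwise stated, summary statistics including the number of subjects (n), mean, standard deviation (SD), median, minimum and maximum will be presented for continuous variables", but it yields where a section states otherwise, as 11 and 11.3 do. The endpoint in SAP 4.2 therefore has no stated summary in units of change.

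**Illustration of what the cells can show.** The plan gives no laboratory figure to reproduce, and SAP 3.5 says the sample size had no statistical basis. All inputs except the subject numbers are assumptions:

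- baseline and follow-up bivariate normal, each with SD 1;
- reference range = baseline mean ± 1.96 SD;
- correlation r = 0.5 to 0.7;
- uniform upward drift d, in SD units;
- n = 50 (one-year minimum), 150 (six-month minimum) and 250 (planned treated) as a range. Month 6 has no scheduled laboratory draw, while early-termination draws are collected, so the number with a post-baseline value is not fixed by the plan.

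Cell probabilities come from the bivariate normal distribution. For n = 150, percent of subjects (expected number):

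| Cell | r = 0.5, no drift | r = 0.5, d = 0.3 | r = 0.7, no drift | r = 0.7, d = 0.3 |
|---|---|---|---|---|
| normal to normal | 90.9% | 90.0% | 91.7% | 90.7% |
| normal to high | 2.0% (3.1) | 4.1% (6.2) | 1.7% (2.5) | 3.6% (5.4) |
| high to normal | 2.0% (3.1) | 1.8% (2.7) | 1.7% (2.5) | 1.3% (1.9) |
| low to normal | 2.0% (3.1) | 2.2% (3.3) | 1.7% (2.5) | 2.0% (3.0) |
| normal to low | 2.0% (3.1) | 0.9% (1.4) | 1.7% (2.5) | 0.7% (1.0) |

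The normal-to-normal share moves by about one percentage point, and normal to high rises by about three subjects.

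The mean change has standard error √(2(1 − r))/√n. For n = 150:

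- r = 0.5: SE = 1/√150 = 0.082; d/SE = 0.3/0.082 = 3.67; power ≈ Φ(3.67 − 1.96) = Φ(1.71) = 96%.
- r = 0.7: SE = 0.775/√150 = 0.063; d/SE = 4.74; power ≈ Φ(2.78) = 99.7%.

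For the shifts, an exact two-sided 5% sign test was applied, first to normal-to-high against high-to-normal only, then to all upward against all downward moves. Ranges run over r = 0.5 to 0.7:

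| n, drift | d/SE | Paired mean | Normal/high shifts | All shifts |
|---|---|---|---|---|
| 50, 0.3 SD | 2.12–2.74 | 56–78% | under 1% | about 3% |
| 150, 0.2 SD | 2.45–3.16 | 69–88% | about 5% | 11–12% |
| 150, 0.3 SD | 3.67–4.74 | 96–99.7% | 12–13% | 23–26% |
| 250, 0.5 SD | 7.91–10.21 | about 100% | 72–80% | 87–93% |

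At n = 50 the t distribution lowers the paired-mean figures by about one point. No such test is planned; power serves here only to measure the information lost by classing.

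**The case against.** The strongest reply is that protocol 7.3.2 permits shift tables and section 7 leaves the full description of the analyses to the SAP. A reader might infer that the SAP departed from the protocol without declaring it. The documents do not support that: choosing one of two permitted options need not appear in SAP 13. What remains is the conflict with the synopsis and an endpoint of change that the chosen summary does not express.

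A reader might also infer that shift tables make a null laboratory result almost certain. That does not hold in general. No laboratory hypothesis test is planned, and the full table shows downward as well as upward moves. With 250 subjects and a 0.5 SD drift, the asymmetry would usually be visible. Nor could a drift in a single-arm study be attributed to M207 on this evidence.

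Third, the data are not lost. Every value is listed, abnormal values are listed again, and clinically significant abnormalities become adverse events, which are tabulated. A single extreme value would be seen with its size. This stands, but listings do not summarise a group change.

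Fourth, absence from the index is imperfect evidence. The index also lacks tables for migraine recurrence and Migraine-ACT responses, which the SAP text promises, and the table shells are a separate document. The point therefore rests mainly on the wording of SAP 11 and 11.3.

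Finally, the protocol gives little reason to expect a drift: its Phase 1 account reports no clinically meaningful laboratory changes, and dosing is per attack. That bears on how likely a finding is, not on whether the endpoint is reported.

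**Conclusion.** The point holds in a limited form. The SAP retains a change-from-baseline laboratory endpoint, the synopsis promises its descriptive statistics, and the stated analysis gives neither the mean change nor its spread. Because protocol 7.3.2 allows the narrower form, this is an unresolved inconsistency and an unreported endpoint, not a clear breach of the protocol.

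The loss matters most for modest drifts and small numbers, and shrinks as either grows. Those figures depend on the assumed normality, reference limits, correlation and drift, none of which the documents supply. The textual conclusion does not depend on them. The change is worth making because it is cheap, not because the laboratory safety evidence would otherwise be void.

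**What to change.** In SAP 11.3, keep the shift tables. Add one table for hematology and one for serum chemistry, giving the actual value and the change from baseline (n, mean, SD, median, minimum, maximum) at the Month 12 or early-termination draw. List them in SAP 17 after 14.3.3.1.1 and 14.3.3.2.1, and align the laboratory sentence in SAP 11. Since SAP 6.1 assigns early-termination data to the nearest visit window, state in the shells whether those draws are pooled with Month 12. A 95% confidence interval for the mean change is optional; the protocol does not ask for one.

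If the sponsor prefers shifts alone, SAP 13 should say so, give the reason, and reconcile the synopsis with protocol 7.3.2.

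The cost is a few lines of SAP text and two standard tables from data already collected. The only downside is a little more output.

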11.4. VITAL SIGNS

All subjects will have vital signs including body temperature (TEMP), respiratory rate (RR), systolic blood pressure (SBP), diastolic blood pressure (DBP) and heart rate (HR)

measured at screening and all subsequent visits. Weight will be collected at selected visits, and height will be collected at screening and final visit only (or early termination visit).

A listing of abnormal vital signs results will be provided using the ranges below. All vital signs measurements will also be listed for each subject.

Vital Sign	Low Cutoff	High Cutoff
Systolic Blood Pressure	90 mmHg	139 mmHg
Diastolic Blood Pressure	60 mmHg	89 mmHg
Heart Rate	50 beats/minute	100 beats/minute
Respiratory rate	12 breaths/minute	20 breaths/minute
Body Temperature	36.1 degrees Celsius	37.5 degrees Celsius

11.5. 12-LEAD ECG

Twelve-lead ECG will be performed at screening, months 6 and 12 study visits. Abnormal ECG results will be listed. All ECG findings collected in the CRF will also be listed.

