6.2. KEY DEFINITIONS

6.2.1. Baseline

Baseline assessment for migraine and headache endpoints will be based upon the data recorded in the eDiary at time 0, prior to the first administration of Investigational Product. Baseline MBS is recorded at Visit 2. For other variables, the baseline assessment will be the latest available valid measurement taken prior to the first administration of Investigational Product.

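### The protocol promises vital signs summarised as observed values and change from baseline; SAP 11.4 gives only listings, and SAP 13 does not declare the departure

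*SAP*

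**What the plan says.** **Protocol.** The Statistical Analyses entry of the synopsis states: "Actual values and changes from baseline for clinical laboratory test results and vital sign measurements will be summarized using descriptive statistics". Protocol 7.3.2 repeats the commitment and adds timing: "Actual values and changes from baseline for assessments of clinical laboratory test results, ECG parameters, and vital sign measurements will be summarized at each visit". That sentence goes on to allow descriptive statistics or shift tables, as appropriate. Protocol 7.1.1 lists change from baseline in vital signs at seven post-baseline visits as a safety endpoint.

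**SAP, endpoint and baseline.** SAP 4.2 keeps that endpoint: "Changes from baseline in vital signs at Months 1, 2, 3, 6, 9, 12, and at the 2-week post-study visit". SAP 6.2.1 supplies the reference value for variables other than the migraine and headache endpoints: "the baseline assessment will be the latest available valid measurement taken prior to the first administration of Investigational Product".

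**SAP, analysis.** SAP 11.4 names two outputs. The first is "A listing of abnormal vital signs results will be provided using the ranges below"; the second lists all measurements by subject. The sentence in SAP 11 that takes the place of the protocol's by-visit commitment reads: "Clinical laboratory test results and ECG parameters will be summarized at each visit using shift tables or listings of abnormal results as appropriate". Vital signs are not in it. For laboratory tests, SAP 11.3 does state a summary: "The number and percentage of subjects with indicated shifts (low, normal, high) in their results from baseline to post-baseline will be presented".

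**SAP, declared changes.** SAP 13 reports changes to efficacy endpoints and nothing on safety.

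**The concern.** SAP 4.2 carries an endpoint that no analysis section delivers, and the protocol's commitment to summarise it has gone without a declaration. Followed literally, the SAP would produce a long-term safety report with no mean, SD or change for blood pressure, heart rate, respiratory rate or temperature at any visit.

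The loss is limited. A vital-sign change judged untoward can be recorded as an adverse event under protocol 8.2.1 and so reach the adverse event tables. What would be missed is a modest average shift spread over many subjects, which a reader would have to rebuild from by-subject listings. In a study whose primary objective is the safety of repeated use over 6 to 12 months, that is a basic display.

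Two related gaps are secondary. The synopsis promises shift tables for ECG parameters, whereas SAP 11.5 gives listings only. SAP 11 permits listings, so the conflict there is with the protocol. Change in physical examination findings is an endpoint in SAP 4.2, but SAP 11.6 only lists the findings; no passage promises a table for it.

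**Working it through.** The main check is a comparison of texts. The arithmetic only gives scale.

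**1. Where the commitment drops out.** In protocol 7.3.2 the by-visit sentence stands between one on serious events and events leading to discontinuation, and one on skin assessments. SAP 11 reproduces both neighbours word for word. The sentence between them has been rewritten: vital signs, observed values, change from baseline and descriptive statistics are all gone.

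**2. Planned vital-sign outputs in the SAP.**

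| Place | Vital-sign output |
|---|---|
| SAP 11.4 | 2 listings (abnormal values; all values) |
| SAP 17, tables | none |
| SAP 18, figures | none (three skin-score figures) |
| SAP 19, listings | 16.2.8.3.1 and 16.2.8.3.2 |
| SAP 13, declared changes | none |

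The table index is weak evidence alone. It also lacks the Migraine-ACT, recurrence and strongest-causality summaries that the SAP text promises. The finding rests on the text of SAP 11 and 11.4.

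**3. Size of the gap.** SAP 11.4 names 5 vital signs (systolic and diastolic pressure, heart rate, respiratory rate, temperature). SAP 4.2 names 7 post-baseline visits. 5 × 7 = 35 change summaries implied; 0 specified.

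**4. What a reader would have to work through.** Take the minimum targets in SAP 3.4 (250 treated, 150 to six months, 50 to one year), no missed visits, and vital signs at all ten visits:
- 50 × 10 + 100 × 7 + 100 × 3 = 1,500 subject-visits
- less 250 if Visits 1 and 2 are combined = 1,250
- × 5 vital signs = 6,250 to 7,500 readings

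This is a floor for treated subjects. Early-termination and post-study visits of the 200 who leave early would add up to 2 × 200 = 400 subject-visits, and the listing is planned on the Screened Population, which is larger.

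**5. What the abnormal listing cannot show.** Largest unflagged rise = high cutoff in SAP 11.4 minus baseline, counting only values above the cutoff as abnormal:
- systolic, baseline 110, 120, 130: 139 − baseline = 29, 19, 9 mmHg
- diastolic, baseline 70, 80: 89 − baseline = 19, 9 mmHg
- heart rate, baseline 60, 70, 80: 100 − baseline = 40, 30, 20 beats/min

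Conversely, hypertension alone does not exclude a subject, because exclusion criterion 15 requires three or more risk factors. A subject with stable raised pressure could be flagged at every visit with no change at all.

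**6. What a table would give.** 95% half-width = t(0.975, n − 1) × SD/√n. The documents give no SD for change in systolic pressure; 8 to 12 mmHg is assumed.
- n = 150: 1.976 × 8/√150 = 1.29; with SD 12, 1.94 mmHg
- n = 50: 2.010 × 8/√50 = 2.27; with SD 12, 3.41 mmHg

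A drift of a few mmHg would therefore be visible in a table.

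**The case against.** The strongest reply is that SAP 6.1 already covers this. Unless otherwise stated, "summary statistics including the number of subjects (n), mean, standard deviation (SD), median, minimum and maximum will be presented for continuous variables". SAP 4.2 names the endpoint, SAP 6.2.1 gives the baseline, and SAP 15.2.5.2 uses systolic blood pressure to illustrate a summary layout. SAP 11.4 never says vital signs will not be summarised, and the table shells are a separate document that may contain the table.

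This shows that a table may have been intended, not that the SAP commits to one. Laboratory values are continuous too, yet SAP 11.3 gives them only shifts and listings, so the SAP's own practice treats 6.1 as a rule on format and not as a source of tables. Section 15.2 is generic: it also refers to an ITT set and to placebo column order, neither of which applies to this single-arm study.

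A second reply is that protocol 7.3.2 allows shift tables, and a low/normal/high shift table would also miss a within-range rise. That is correct. Step 5 shows why a cutoff display cannot replace change from baseline; it does not measure the loss against a shift table. But no vital-sign shift table is planned either, and the synopsis specifies descriptive statistics without that alternative.

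Third, laboratory results have a similar mismatch with the synopsis, which promises descriptive statistics for them as well. This is fair. There, however, 7.3.2 permits the shift tables that SAP 11.3 provides.

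Finally, the consequence is bounded. A single arm cannot attribute a drift to treatment, and clinic visits are not timed to dosing. This stands, and it is why the point concerns a missing descriptive summary and not a concealed harm.

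**Conclusion.** The concern holds. The SAP leaves a retained safety endpoint, under the primary objective, without a specified summary, and departs from the protocol without saying so in SAP 13. The gap is 35 implied change summaries against none specified. This conclusion needs no assumption beyond the texts, except that the unseen shells cannot be relied on to supply what the SAP omits.

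No size of drift is claimed. The only blood-pressure change the documents report (Phase 1, protocol 1.2.1) was 3 to 12 mmHg, acute, and near baseline at 1 hour in all M207 groups. The precision figures depend on the assumed SD of 8 to 12 mmHg. The point should be fixed before database lock; it does not undermine the study design.

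**What to change.** 1. **Main change.** Add to SAP 11.4 and the table index a Safety Population table of observed values and change from baseline for systolic and diastolic pressure, heart rate, respiratory rate and temperature at Months 1, 2, 3, 6, 9 and 12 and the post-study visit, with n at each, using the SAP 6.2.1 baseline. Otherwise, declare and justify the omission in SAP 13 and align SAP 4.2.
2. **Secondary.** Add simple shift tables from baseline to Months 6 and 12 for ECG interpretation and overall physical examination finding, or declare the ECG change in SAP 13.
3. **Optional, not an error.** Tabulate diary skin reactions for the 1st, 5th, 15th and 25th treated attack, with the number of subjects at each. The diary tables in SAP 11.2.1 take the worst grade per subject or pool all attacks, so they cannot show a trend with repeated application. Investigator ratings by visit (SAP 11.2.2) cover this in part.

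**Cost.** One vital-sign table, two small shift tables and one optional skin table, all from data already collected, with no protocol change.

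**Limits.** The vital-sign table would be descriptive and would largely miss an acute post-dose rise. In the skin table, later columns would be small and selected. For example, at 2 treated attacks per 28 days the 25th attack falls on day 28 × 25/2 = 350, after the Month 12 visit on day 336, so subjects treating at that rate would not reach it.
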